Time Windows	--	+ 8 to 10 days	+ 28 to 35 days	+ 28 to 35 days	+ 8 to 10 days	+ 28 to 35 days
Informed consent/assent ^a	X					
Inclusion & Exclusion Criteria	X					
Demographic data	X					
Medical history	X					
Influenza vaccination history	X					
History-directed physical examination	X			X		
Temperature ^b	X			X		
Review contraindications for vaccination				X		
Allocation of subject number	X					
Blood sample (BL) ^c	BL1		BL2			BL2
Vaccination ^d	X			X		
Immediate surveillance (20 minutes)	X			X		
Diary card (DC) provided	DC1			DC2		
Telephone contact ^e		X			X	
Diary card reviewed and collected			DC1	DC1		DC2
Interim history			X	X		X
Termination record ^f			X			X
Serious adverse events	To be reported throughout the study period					

^a Informed consent form will be signed and dated by parent(s) or guardian(s) for subjects 6 months to < 9 years of age and assent form will be signed and dated by subjects 7 to < 9 years of age.

^b The preferred route for this study is rectal for subjects 6 to < 36 months of age, and oral for subjects 3 to < 9 years of age. The axillary route may be used when a rectal or oral temperature cannot be obtained.

^c A blood sample, approximately 5 mL, will be collected from all subjects at Visit 1, prior to vaccination, and at either Visit 2 (for subjects receiving 1 influenza vaccine dose) or at Visit 3 (for subjects receiving 2 influenza vaccine doses).

^d One or 2 doses of influenza vaccine will be administered according to the Advisory Committee on Immunization Practices guidance in effect during the study. If 2 doses of influenza vaccine are indicated, 1 dose will be administered during Visit 1 and the second dose (same 0.25-mL or 0.5-mL volume of Fluzone Quadrivalent vaccine as administered at Visit 1) will be administered approximately 28 days later during Visit 2.

^e The subject's parent/guardian will be contacted by telephone on Day 8 (window, Days 8–10) after vaccination as a reminder to complete the diary card and to bring it with them to the next visit. The termination form will be completed at Visit 2 for subjects receiving 1 dose of influenza vaccine or at Visit 3 for subjects receiving 2 doses of influenza vaccine.

Study Flow Chart for Subjects ≥ 18 Years of Age: 2 Visits, 1 Vaccination

Visit Number	Visit 1	Telephone Contact	Visit 2
Study Timelines	Day 0	Visit 1 + 8 days	Visit 1 + 21 days
Time Windows		+ 8 to 10 days	+ 21 to 28 days
Informed consent	X		
Inclusion/exclusion criteria	X		
Demographic data	X		

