- 14) Within 30 minutes of removing the assigned vaccine from the refrigerator, inject 1 dose of assigned study vaccine intramuscularly into the anterolateral muscle of the thigh or the deltoid muscle, as appropriate (see Section 6.1.1.2 and Section 6.1.2.2).
- 15) Observe subject for 20 minutes following the injection for the occurrence of allergic and anaphylactic reactions and immediate injection site and systemic reactions.
- 16) Provide to the subject or subject's parent/guardian an age-appropriate diary card, a digital thermometer, and a flexible ruler, along with instructions for their use, to record solicited injection site and systemic reactions from Day 0 through Day 7 post-vaccination, and unsolicited AEs, SAEs, as well as any concomitant medications (see Section 6.7) from Visit 1 through Visit 2.
- 17) Schedule Visit 2.
- 18) Remind the subject or subject's parent/guardian that they will be contacted by telephone on or about Day 8 post-vaccination to remind them to complete the diary card and to bring the completed diary card with them to Visit 2.
- 19) Remind the subject or subject's parent/guardian to notify the site immediately if an SAE occurs.
- 20) Complete the relevant electronic case report form (eCRF) pages for this visit.

Telephone Contact – Visit 1 + 8 (window, 8–10) days

Eight days after the study vaccination at Visit 1, a delegated staff member from the study site will telephone the subject or subject's parent/guardian to perform the following:

- 1) Remind the subject or subject's parent/guardian to record on the diary card any AEs and any concomitant medications (see Section 6.7) from Visit 1 until Visit 2.
- 2) Remind the subject or subject's parent/guardian to notify the site immediately if an SAE occurs. If an SAE occurs, follow the instructions in Section 10 for reporting it.
- 3) Confirm the date of the appointment of Visit 2, instruct the subject or subject's parent/guardian to return at this time, and to bring the completed diary card with them to the study site.

Note: If Day 8 falls on a weekend or a holiday, the telephone call may be placed preferably on the following business day. If the subject or subject's parent/guardian is not available, the study staff should document the attempts to make contact.

Visit 2 (Visit 1 + 21 [window, 21–28] days) – Subjects 18 Years of Age and Older – Collection of Safety Information and Blood Sample

- 1) Review the diary card with the subject and collect it as a source document.

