- 4) Complete the relevant eCRF pages for this visit as well as the termination record in the eCRF.

Collection of Diary Cards

If the subject or subject's parent/guardian does not return for Visit 2 or Visit 3, and the diary card is not received at the site, site personnel will contact the subject or subject's parent/guardian by telephone. During the telephone call, the subject or subject's parent/guardian will be reminded to return the diary card to the study site. Telephone calls will be recorded on the subject's source documents. If study personnel are unable to contact the subject or subject's parent/guardian by telephone with 3 attempts, study personnel will follow instructions given in Section 5.2.9.

Serious Adverse Events and Adverse Events That Are Related to Vaccination or That Led to Discontinuation:

At any time during the study, a subject who experiences an SAE or an AE must be followed if *either* of the following is true:

- The SAE or AE is considered by the Investigator to be related to vaccination, and is not resolved by the end of the subject's participation in the study
- The subject has been discontinued from the study because of the SAE or AE

Any such subject must be followed until the condition resolves, becomes stable, or becomes chronic.

^a As per ACIP guidance

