5.1.6 Early Safety Data Review

This study will not include an early review of safety data. However, it may be interrupted at any time if new data about the investigational products become available, and/or on advice of the Sponsor, the IRB(s), or the FDA.

If the study is prematurely terminated or suspended, the Sponsor will promptly inform the Investigators, the IRB(s), and the regulatory authorities of the reason for termination or suspension. If the study is prematurely terminated for any reason, the Investigator will promptly inform the study subjects or subjects' parents/guardians, as appropriate, and should assure appropriate therapy and follow-up.

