5.2.11 Follow-up of Discontinuations

The site should complete all scheduled safety follow-ups and contact any subject who has prematurely terminated the study because of an SAE, other type of AE, non-compliance with the protocol, or loss of eligibility, including definitive contraindications.

For subjects where the reason for early termination was lost to follow-up or if the subject withdrew informed consent and specified that they do not want to be contacted again and it is documented in the source document, the site will not attempt to obtain further safety information.

For subjects where the reason for early termination is voluntary withdrawal, the site will attempt to contact them except if they specified that they do not want to be contacted again and it is documented in the source document.

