9.3.1.3.2 Reactogenicity (Solicited Reactions From Day 0 Through Day 7 After Each Vaccination)

After each vaccination, subjects or subject's parent/guardian will be provided with a safety diary card, a digital thermometer, and a flexible ruler, and will be instructed how to use them. The following items will be recorded by the subjects in the diary card on the day of vaccination and for the next 7 days (i.e., Day 0 through Day 7) until resolution:

- Daily temperature, with the route by which it was taken
- Daily measurement or intensity grade of all other solicited injection site and systemic reactions
- Action taken for each event, if any (e.g., medication)

The action taken by the subject or subject's parent/guardian to treat any **solicited reactions** will be classified in the eCRF using the following scale:

0: None

1: Medication (self-medication with an existing prescription or over-the-counter medication)

2: Health care provider contact (no new medication prescribed)

- 3: Health care provider contact and prescription of a new medication (health care provider instructed subject to take a new medication, either an over-the-counter medication or one requiring a written prescription)
- 4: Hospitalization (inpatient)

Subjects or subject's parent/guardian will be contacted by telephone 8 days after each vaccination to remind them to record all safety information in the diary card.

If the timing of the telephone call should fall on a weekend or a holiday, the call should be made on the next business day. If contact is not made on the designated day, study staff will continue calling until contact is made. Every telephone attempt and its outcome will be documented in the source document.

Table 9.1, Table 9.2, Table 9.3, Table 9.4, and Table 9.5 present the injection site reactions and systemic reactions that are prelisted in the diary cards and eCRF, together with the intensity scales.

Table 9.1: Solicited Injection Site Reactions: Terminology, Definitions, and Intensity Scales (Subjects 6 to < 36 Months of Age)

CRF term (MedDRA lowest level term [LLT])	Injection site tenderness	Injection site erythema	Injection site swelling
Diary card term	Tenderness	Redness	Swelling

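### Neither the Day 8–10 call nor the missed-visit call asks whether an SAE or AESI has occurred, so detection before the next visit depends on the family volunteering it

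*Protocol*

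**What the plan says.** **The Day 8–10 call.** Protocol 9.3.1.3.2 says that subjects or parents "will be contacted by telephone 8 days after each vaccination to remind them to record all safety information in the diary card". The paediatric flow chart describes it "as a reminder to complete the diary card and to bring it with them to the next visit"; the adult flow chart and the synopsis are to the same effect. Protocol 5.1.4 gives staff three tasks, repeated for the call after a second dose:
- "Remind the subject or subject's parent/guardian to record on the diary card any AEs and any concomitant medications"
- "Remind the subject or subject's parent/guardian to notify the site immediately if an SAE occurs", followed by "If an SAE occurs, follow the instructions in Section 10 for reporting it"
- confirm the next appointment.

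**The missed-visit call.** Under Collection of Diary Cards in 5.1.4, if the visit is missed and no card has arrived, the site telephones and "the subject or subject's parent/guardian will be reminded to return the diary card to the study site". After three failed attempts, 5.2.9 applies.

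**Active questioning.** Protocol 9.3.1.3 has staff ask about reactions and AEs at each visit. Before that, 9.3.1.3.1 provides 20 minutes of observation after each vaccination.

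**After loss to follow-up.** Protocol 5.2.11 states that for these subjects "the site will not attempt to obtain further safety information".

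**Safety oversight.** Protocol 5.1.6: "This study will not include an early review of safety data".

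**Analysis.** SAP 5.1.3.1 divides unsolicited AEs by all subjects vaccinated at the dose, and solicited reactions by subjects with non-missing data.

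**The concern.** Staff already speak to each family just after the Day 0–7 solicited window closes, and nothing is asked. Until the next visit, an SAE or AESI reaches the site only if the family volunteers it.

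That is a weak route for some listed events. Protocol 9.3.1.1 and 9.3.1.3.5 treat Bell's palsy, febrile convulsions in children and hypersensitivity or allergic reactions as SAEs whether or not the subject was hospitalised. A parent told to ring about an SAE may not realise that a brief convulsion or an allergic reaction managed at home qualifies, and the call script does not list these events. Protocol 1.3.2 also places the fever-associated seizure risk on the day of vaccination and the day after, so such an event would be over by the time of the call.

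Two things are at stake. The 24-hour SAE report required by Protocol 10.1 cannot start until the site knows of the event, and no early safety review exists to catch it. And a subject who drops out of sight after the call is counted as having had no unsolicited AE, although staff could have asked.

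**Working it through.** The plan states no figure on this point, so there is none to reproduce. The check is a calendar calculation plus an illustration of the denominator effect.

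**1. Interval with no scheduled safety question.** Inputs: call window Days 8–10; Visit 2 on Day 21–28 (adults); next visit Day 28–35 after each dose (children).
- From vaccination: 21–28 days (adults), 28–35 days (children).
- From call to visit, adults: 21 − 10 = 11 to 28 − 8 = 20 days.
- From call to visit, children: 28 − 10 = 18 to 35 − 8 = 27 days.

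Across both, a question at the call comes 11 to 27 days before the visit.

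**2. Denominator effect for unsolicited AEs.** Assume a fraction *f* of a 60-subject group is never reached again, returns no card and volunteers nothing, and that such loss is unrelated to events. The expected reported percentage is then the true percentage × (1 − *f*). With zero events, the exact 95% upper limit is 1 − 0.025^(1/n). The documents give no non-return rate, so *f* is shown over a range.

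| Assumed *f* | Subjects with data | True 20% reported as | Upper limit as planned (0/60) | Upper limit on subjects with data |
|---|---|---|---|---|
| 5% | 57 | 19% | 5.96% | 6.27% |
| 10% | 54 | 18% | 5.96% | 6.60% |
| 20% | 48 | 16% | 5.96% | 7.40% |

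The chance of seeing at least one event with a true rate of 2% is 1 − 0.98^60 = 70.2% with 60 subjects followed, and 1 − 0.98^54 = 66.4% with 54.

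SAP 5.1.3.1 gives avoiding under-estimation as the reason for using subjects with documented safety, then sets the unsolicited denominator to everyone vaccinated. Solicited reactions are not diluted in this way.

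**3. Could call answers stand in for a missing diary?** SAP 4.4.1.1.1, step 1, turns an Investigator's No with all daily records missing into intensity None (fever excepted), so that subject enters the denominator as reaction-free. A Yes with no grade or measurement has no conversion rule; intensity and presence stay Missing, and SAP 4.4.1.1.3 drops the subject. Keeping the No answers while losing the Yes answers would push solicited rates down, so the call should not be used for this.

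**The case against.** The plan does more than a quick reading suggests, and three stronger readings fail.

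- **A reader might infer that a subject who never returns yields no data.** The documents do not support this. The site telephones to recover the card (5.1.4); calls and certified mail follow, at least to learn the subject's health status (5.2.9); and most discontinuations are still followed for safety (5.2.11). Loss to follow-up in 5.2.10 means that contact could not be established. Day 0 observations and volunteered SAEs are kept. What stands is narrower: the missed-visit call has no event question, and 5.2.9 requires the efforts to be documented without specifying any.
- **A reader might infer that solicited reactions are first asked about at the visit.** They are not. The diary card asks for them daily, Day 0 through Day 7, with prelisted terms and scales. The gap concerns SAEs and AESIs outside those terms.
- **A reader might infer that SAE reports will be late.** This is not shown. Families are told at vaccination and again at the call to notify the site at once, and the script sends staff to Section 10 if an SAE occurs. But that line says how to report an SAE, not to ask about one.

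Protocol 11.1 also mentions interviews at specified intervals, but the only questioning times the protocol specifies are the visits. The diary card and consent form are not available here and may list the AESIs. Finally, the vaccines are licensed and the study is descriptive, which limits the weight of the point.

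**Conclusion.** The point holds as a gap in ascertainment. The Day 8–10 and missed-visit calls are scripted without any question about SAEs or AESIs, and for 21–28 days in adults and 28–35 days after each dose in children, detection rests on the family volunteering the event. Asking at the existing call would bring an unvolunteered event forward by 11 to 27 days.

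The denominator effect is confined to subjects who are never reached again and whose card never arrives. Its size depends entirely on an assumed rate: at 5%, one percentage point on a true 20%. Any count of subjects whose data would be gained is likewise an assumption. SAP 5.1.3.1 states no separate denominator for SAEs; if the unsolicited rule is used, the same effect applies.

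No sample size or power figure is affected. This is a cheap improvement, not a flaw that undermines the study.

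**What to change.** In Protocol 5.1.4 (both telephone contacts and Collection of Diary Cards) and 9.3.1.3.2:
- Add a scripted question: since vaccination, has there been any SAE, any listed AESI (read out in lay terms), any hospitalisation or any medical visit?
- Record the answer with dates in source and, for any event, in the eCRF. Protocol 11.1 already allows information absent from the diary card to take this path.
- Start Section 10 reporting on any positive SAE or AESI answer.
- State that call answers do not replace diary data for solicited reactions, for the reason in step 3 of the working.
- While editing, reconcile 9.3.1.3.2, which has staff keep calling until contact is made, with 5.1.4, which asks only that attempts be documented.

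**Cost.** No new scheduled contact: a few minutes on 240 first-dose calls and at most 60 + 60 = 120 second-dose calls, plus protocol wording and eCRF entry for positive answers. Prompting may slightly raise AE reporting, and not necessarily equally: parents report for young children, adults report for themselves, and two-dose children get two calls.

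**Limit.** Subjects who miss the call and are never reached still count as event-free. That denominator rule is a separate SAP matter.

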9.3.1.3.4 Serious Adverse Events

Information on SAEs will be collected and assessed throughout the study, from Visit 1 through Visit 2 for subjects receiving 1 dose of study vaccine, and from Visit 1 through Visit 3 for subjects receiving 2 doses of study vaccine.

Any SAE occurring at any time during the study will be reported by the Investigator through the EDC system and according to the completion guidelines provided by the Sponsor. All information concerning the SAE is to be reported, either as part of the initial reporting or during follow-up reporting if relevant information became available later (e.g., outcome, medical history, results of investigations, copy of hospitalization reports). The Investigator will assess the causal relationship between the SAE and the investigational product as either “Not related” or “Related”, as described in Section 9.3.1.3.6.

See Section 10 for further details on SAE reporting.

9.3.1.3.5 Adverse Events of Special Interest

Adverse events of special interest will be captured as SAEs. These include new onset of GBS, encephalitis/myelitis (including transverse myelitis), neuritis (including Bell’s palsy, optic neuritis, and brachial neuritis), thrombocytopenia, vasculitis, convulsions (including febrile convulsions [children only]), and anaphylaxis or other hypersensitivity/allergic reactions from Visit 1 through Visit 2 for subjects receiving 1 dose of vaccine, or from Visit 1 through Visit 3 for subjects receiving 2 doses of vaccine.

9.3.1.3.6 Assessment of Causality

The Investigator will assess the *causal relationship* between each unsolicited systemic AE and vaccination as either not related or related, based on the following definitions^a:

- 0: Not related – The AE is clearly/most probably caused by other etiologies such as subject’s underlying condition, therapeutic intervention, or concomitant therapy; or the delay between vaccination and the onset of the AE is incompatible with a causal relationship; or the AE started before the first vaccination (screening phase, if applicable)

^a ICH Guidelines, Clinical Safety Data Management E2A

1: Related – There is a “reasonable possibility” that the AE was caused by the vaccination, meaning that there is evidence or arguments to suggest a causal relationship

Note: By convention, all injection site AEs (solicited and unsolicited) and all solicited systemic reactions are considered to be related to vaccination and referred to as reactions, and therefore do not require the Investigator’s opinion on relatedness.

AEs likely to be related to the product, whether serious or not, that persist at the end of the study will be followed up by the Investigator until their complete disappearance or the stabilization of the subject’s condition. The Investigator will inform the Sponsor of the date of final disappearance of the event.

9.3.2 Immunogenicity

The observational immunogenicity objective is presented in Section 2.1.2.

9.3.2.1 Immunogenicity Endpoints

Immunogenicity will be evaluated in all subjects by analyzing sera collected prior to vaccination on Day 0 (Visit 1) and after final vaccination (28 [window, 28–35] days post-final vaccination for subjects 6 months to < 9 years of age [Visit 2 for subjects receiving 1 dose; Visit 3 for subjects receiving 2 doses]; or 21 [window, 21–28] days post-vaccination for subjects \geq 18 years of age) using the HAI assay technique.

For each influenza vaccine strain (i.e., 3 strains for Fluzone High-Dose vaccine [a trivalent vaccine] and 4 strains for Fluzone Quadrivalent vaccine), HAI assay titers at pre-vaccination (Day 0) and after the final vaccination will be determined in duplicate.

The derived endpoints^a are:

- Geometric means of HAI assay titers at pre-vaccination and post-final vaccination
- Ratios of post-final vaccination titers divided by pre-vaccination titers.
- Seroprotection: a titer \geq 40 (1/dilution [dil]) at pre-vaccination and at post-final vaccination
- Seroconversion: either a pre-vaccination titer $<$ 10 (1/dil) and a post-final vaccination titer \geq 40 (1/dil), or a pre-vaccination titer \geq 10 (1/dil) and a \geq 4-fold increase in post-final vaccination titer

^a Post-final vaccination in each of the derived endpoints is defined as 28 (window, 28–35) days post-final vaccination for subjects 6 months to < 9 years of age, and 21 (window, 21–28) days post-vaccination for subjects \geq 18 years of age

9.3.2.2 Immunogenicity Assessment Methods

Anti-influenza antibodies will be measured by HAI assay performed by Sanofi Pasteur’s GCI department or an external testing laboratory under GCI’s supervision. Serum samples and quality control sera (sheep and/or human sera) will be incubated with Sigma Type III NA to eliminate non-specific inhibitors. Adsorption of spontaneous anti-species agglutinins will be performed by incubating the serum samples and quality control sera with a red blood cell (RBC) suspension. Following this, the mixtures will be centrifuged and the supernatants containing the treated sera

will be collected for testing. Ten 2-fold dilutions (starting at 1/10) of the treated serum samples and quality control sera will be incubated with a previously titrated influenza virus at a concentration of 4 hemagglutination unit/25 μ L. Influenza virus will not be added to the serum control wells containing only serum and RBCs. The mixture will be incubated and a RBC suspension will be added. Following incubation, the results will be read. The endpoint of the assay is the highest serum dilution in which complete inhibition of hemagglutination occurred. Each serum sample will be titrated in independent duplicates, and the 2 values, which do not differ by more than one 2-fold dilution, will be reported. The geometric mean titer between the 2 values will be calculated after the release of the data to the Clinical Data Management (CDM) platform. The lower limit of quantification (LLOQ) for HAI is set at 10, the lowest serum dilution used in the assay (i.e., 1/10). Titers below this level are reported as < 10. If the highest/last serum dilution used in the assay exhibits complete inhibition of hemagglutination, the serum antibody titer will be reported as \geq 10240 (1/dil).

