11.2 Data Management

Management of Clinical Data

Data generated during the study will be managed following 2 different processes:

- Clinical data, defined as all data reported in the eCRF, and laboratory data will be handled by the Sponsor's CDM platform or authorized representative.
- Data pertaining to SAEs, which are reported by the Investigator on the eSAE forms or SAE reporting forms, will be handled by the Sponsor's GPV Department.

During the study, clinical data reported in the eCRFs will be integrated into the clinical database under the responsibility of the Sanofi Pasteur CDM platform. Data monitoring at the sites and quality control in the form of computerized logic and/or consistency checks will be systematically applied in order to detect errors or omissions. In addition, data reviews may be performed several times by the Sponsor's staff in the course of the study. Any questions pertaining to the reported clinical data will be submitted to the Investigator for resolution using the EDC system. Each step of this process will be monitored through the implementation of individual passwords to maintain appropriate database access and to ensure database integrity.

The validation of the immunogenicity data will be performed at the laboratory level following the laboratory's procedures. Information from the laboratory will be checked for consistency before integration into the clinical database.

After integration of all corrections in the complete set of data, and after the SAE information available from CDM and the GPV Department has been reconciled, the database will be released for statistical analysis.

Serious Adverse Event Data Management

During the study, data pertaining to SAEs reported on eSAE forms will be integrated into the Sponsor's centralized GPV database.

Upon receipt of an eSAE form, the data will be entered into the GPV database after a duplicate check. Each SAE case will be assigned a case identification number. Each case will be entered in the GPV database and assessed by the case management platform or its delegate before being reported to the relevant authorities as necessary. Assessment of related cases will be done in collaboration with the Product Safety Officer and the RMO. Follow-up information concerning a completed case will be entered into the GPV database, and a new version of the case will be created.

The information pertaining to SAEs in the GPV database will be reconciled with that in the clinical database.

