12.3.2 Immunogenicity

For the computations, LLOQ and upper limit of quantification (ULOQ) will be managed as follows:

- If a titer is < LLOQ, then LLOQ/2 will be used
- If a titer is \geq LLOQ and < ULOQ, then the titer itself will be used
- If a titer is \geq ULOQ, then ULOQ will be used

Missing data will not be imputed. No search for outliers will be performed.

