##### **4.3.2.2 Immunogenicity Assessment Methods**

See Section 9.3.2.2 of the protocol for immunogenicity assessment methods.

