**Table 5.1: Descriptive Statistics Produced**

Baseline characteristics and follow-up description	Categorical data	Number of subjects Percentage of subjects
	Continuous data	Mean, standard deviation (SD), quartiles, minimum, and maximum
Clinical safety results	Categorical data	Solicited: Number and percentage (95% confidence intervals [CIs]) of subjects Unsolicited: Number and percentage (95% CIs) of subjects, and number of events
Immunogenicity results	Categorical data (seroprotection, seroconversion, cutoff)	Number and percentage (95% CIs) of subjects
	Continuous data (titer / data)	$\text{Log}_{10}$ : Mean and SD Anti- $\text{Log}_{10}$ (work on $\text{Log}_{10}$ distribution, and anti- $\text{Log}_{10}$ applied): Geometric mean, 95% CI of the geometric mean, quartiles, minimum, and maximum. Graphical representation by reverse cumulative distribution curves (RCDCs)

The confidence interval (CI) for the single proportion will be calculated using the exact binomial method (Clopper-Pearson method, quoted by Newcombe [1]; i.e., using the inverse of the beta integral with SAS®).

For immunogenicity results, assuming that  $\text{Log}_{10}$  transformation of the titers/data follows a normal distribution, at first, the mean and the 95% CI will be calculated on  $\text{Log}_{10}$  (titers/data) using the usual calculation for normal distribution (using Student's t distribution with n-1 degree of freedom), then antilog transformations will be applied to the results of calculations, in order to provide geometric means (GMs) and their 95% CI.

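### Protocol 9.3.2.2: ten 2-fold HAI dilutions from 1/10 end at 1/5120, but a fully inhibited last dilution is reported as ≥10240, and the ULOQ has no number of its own

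*Protocol*

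**What the plan says.** Protocol 9.3.2.2 sets the dilution series as "Ten 2-fold dilutions (starting at 1/10) of the treated serum samples and quality control sera". It ties the lower limit to the same starting point: the LLOQ "for HAI is set at 10, the lowest serum dilution used in the assay (i.e., 1/10"). The titer is defined as the highest dilution showing complete inhibition. For the top of the range it says: "If the highest/last serum dilution used in the assay exhibits complete inhibition of hemagglutination, the serum antibody titer will be reported as" ≥10240 (1/dil).

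Each serum is run in duplicate. The two values may differ by at most one 2-fold step, and "The geometric mean titer between the 2 values will be calculated after the release of the data".

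The SAP adds no assay detail. Section 4.3.2.2 reads "See Section 9.3.2.2 of the protocol for immunogenicity assessment methods". Protocol 12.3.2 caps high titers with the rule that for any titer at or above the "ULOQ, then ULOQ will be used". SAP 4.4.2.1, 4.4.2.3 and 5.3.2 apply the same kind of cap. None of these sections gives the ULOQ a value, whereas the LLOQ is stated as 10.

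For continuous titer data, SAP Table 5.1 lists the geometric mean and "95% CI of the geometric mean, quartiles, minimum, and maximum. Graphical representation by reverse cumulative distribution curves (RCDCs").

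**The concern.** Within one section, the number of dilutions and the ceiling disagree by one doubling. The ceiling is the only figure in either document from which a programmer could set the ULOQ, so the discrepancy can pass straight into the analysis data.

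If ten dilutions are run and 10240 is the constant, a replicate fully inhibited at 1/5120 is recorded as though it had been tested at 1/10240. That value enters the GMTs, the titer ratios, the maximum and the upper end of the reverse cumulative distribution curve. For subjects with very high baseline titers it can also change the seroconversion indicator.

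Taken literally, the section has two further consequences:

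- A single reading of 5120 can never be reported; readings jump from 2560 to ≥10240.
- Duplicates in adjacent wells, 2560 and the last well, would be recorded two 2-fold steps apart and would appear to fail the one-step agreement rule.

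SAP 4.4.2.3 also says its fold-rise algorithm generally keeps the numerator small for extreme values. A post-vaccination value set above the last well tested works against that.

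**Working it through.** **Inputs.** Ten dilutions, 2-fold steps, first dilution 1/10, ceiling report ≥10240 (all Protocol 9.3.2.2); 60 planned subjects per group (Protocol 12.5). The documents give no titer distribution, so every count of ceiling sera below is an assumption.

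**1. The series.** The k-th dilution is 10 × 2^(k−1), giving 10, 20, 40, 80, 160, 320, 640, 1280, 2560, 5120.

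- Tenth dilution: 10 × 2^9 = 5120.
- Stated ceiling: 10240 = 10 × 2^10, the eleventh dilution.
- Ratio: 10240 / 5120 = 2.

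**2. Readings that would reproduce 10240.**

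- Ten doublings after a 1/10 well: 10 × 2^10 = 10240, but this is eleven dilutions.
- Ten dilutions starting at 1/20: 20 × 2^9 = 10240, but this contradicts the 1/10 start and the LLOQ of 10.
- Reporting the next, untested step above 1/5120: contradicts the definition of the titer as the highest dilution with complete inhibition.

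**3. Effect on a GMT**, comparing ULOQ = 10240 with ULOQ = 5120 when the last well is 1/5120. Let q be the share of sera with both replicates at the ceiling, and m the share with one replicate there and one at 2560 (if such pairs are accepted). A serum with both at the ceiling shifts by a factor of 2. A mixed pair moves from √(2560 × 5120) = 3620 to √(2560 × 10240) = 5120, a factor of √2. The group GMT is multiplied by 2^(q + m/2).

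| Sera out of 60 | Both at ceiling | Mixed pair |
|---|---|---|
| 1 | 2^(1/60) = 1.0116 (+1.2%) | 2^(1/120) = 1.0058 (+0.6%) |
| 3 | 2^(3/60) = 1.0353 (+3.5%) | 2^(3/120) = 1.0175 (+1.7%) |
| 6 | 2^(6/60) = 1.0718 (+7.2%) | 2^(6/120) = 1.0353 (+3.5%) |

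Three of each: 2^(4.5/60) = 1.0534 (+5.3%).

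**4. Effect on the geometric mean titer ratio.** This changes by the post-vaccination factor divided by the baseline factor. With 3 post-vaccination and 1 baseline serum having both replicates at the ceiling: 2^(2/60) = 1.0234 (+2.3%).

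**5. Effect on the maximum.** One serum with both replicates at the ceiling moves it from 5120 to 10240.

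**6. Effect on seroconversion.** Among all same-well and adjacent-well duplicate pairs, the 4-fold criterion changes from No to Yes in three combinations only:

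| Baseline | Post-vaccination pair | Ratio, ULOQ 5120 | Ratio, ULOQ 10240 |
|---|---|---|---|
| 1280 | mixed | 3620/1280 = 2.83 | 5120/1280 = 4.00 |
| 1810 | both at ceiling | 5120/1810 = 2.83 | 10240/1810 = 5.66 |
| 2560 | both at ceiling | 5120/2560 = 2.00 | 10240/2560 = 4.00 |

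Each such subject moves the rate by 1/60 = 1.7 percentage points.

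**7. Scale.** If the log10 SD is 0.4 to 0.7 (assumed), the 95% CI of a GMT with n = 60 extends by a factor of 10^(2.001 × 0.4/√60) = 1.27 to 10^(2.001 × 0.7/√60) = 1.52 in each direction. The largest GMT factor in step 3, 1.07, is well inside that.

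**The case against.** The strongest reply is that the wording is loose, not the ceiling. A 1/10 dilution is not itself a 2-fold dilution, so the phrase could mean a 1/10 starting well followed by ten doublings. That lands exactly on 10240 and leaves 1/10 as the lowest dilution. The exact match makes this plausible, and the documents cannot exclude it. But it requires eleven dilutions, and counting 1/10 as the first of ten remains the more natural reading. If the laboratory does run eleven, the ceiling stands and only the count needs correcting.

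It is also fair that any effect on results needs three things the documents do not establish: that the laboratory stops at 1/5120, that it nevertheless reports ≥10240, and that some sera reach the ceiling. Protocol 11.2 states that "validation of the immunogenicity data will be performed at the laboratory level", which may catch the error. It does not tell the reader of the plan which ceiling applies.

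Ceiling values are censored in any case: a serum fully inhibited at 1/5120 may truly exceed 10240. The comparison here is therefore with substituting 5120, not with the true titer. The mixed-pair figures depend on whether such pairs pass the agreement rule, and baselines of 1280 to 2560 combined with a ceiling response may be rare. Finally, a programmer could infer 10240 as the ULOQ without a label. That is true, but it is the disputed figure that would be inferred.

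**Conclusion.** The concern holds. As written, the count of ten, the 1/10 start and the ≥10240 ceiling cannot all be correct, and no other section of the protocol or SAP settles which is wrong. The textual mismatch is certain; any effect on results is conditional.

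The likely consequence is small: a few percent on a GMT under the assumed ceiling counts, a doubled maximum, and at most an occasional change in a seroconversion indicator. Seroprotection at ≥40 is untouched. No hypothesis is tested, so no inferential conclusion is at risk. There is no effect if no serum reaches the ceiling or if the series does extend to 1/10240. This is a point to tidy before the derivation program is finalised, not a flaw in the design.

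**What to change.** Confirm the dilution series with the testing laboratory, then correct one figure in Protocol 9.3.2.2:

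- if ten dilutions are run, keep the count, report a fully inhibited last dilution as ≥5120 and set ULOQ = 5120; or
- if the series reaches 1/10240, change the count to eleven and set ULOQ = 10240.

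Label that value as the ULOQ in 9.3.2.2, as is already done for the LLOQ, and use it as the constant in the derivations under SAP 4.4.2.1, 4.4.2.3 and 5.3.2.

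The cost is one corrected sentence and one checked constant, with no extra testing. If the protocol change is handled as an administrative amendment, Protocol 5.4 requires notifying the IRB(s) and regulatory authorities but not IRB approval. Confirming the series and writing the number into the SAP would protect the analysis in the meantime.
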